7.3 PLANNED ANALYSES

7.3.1 Primary analyses

The primary endpoint (measured from date of randomisation to end of observation period) is:

- Time to first MBE/CRNMBE

as determined by the IAC. It will be analysed using the stratified Cox proportional hazards regression model including factors for age (<80 or ≥80 years old) and treatment arm (110mg DE-DAT vs warfarin-TAT and 150mg DE-DAT vs warfarin-TAT). Models will be fitted for each comparison separately.

The primary analysis will be performed under the intention-to-treat framework on the full analysis set of patients (FAS) that includes all randomised patients (regardless of whether they have received treatment). Patients who discontinue study medication will be followed until the end of the trial. Patients who are lost to follow-up for vital status will be censored for the primary endpoint at the time of their last known vital status. All patients will be analysed according to the treatment arm to which they were randomised.

For the comparison of 110mg DE-DAT vs warfarin-TAT, patients of all ages and geographical regions will be included. For the comparison of 150mg DE-DAT vs warfarin-TAT, patients from the EU/ROW who are ≥80 years old will be excluded from the warfarin-TAT arm (as patients who are ≥80 years old from the EU/ROW are not randomised to 150mg DE-DAT).

The robustness of the primary analysis will be assessed by an on-treatment analysis. This on-treatment analysis will only count events that occur while a patient is taking study medication (including the REP of 6 days – see [Section 5.2.2.2](#)). It will also analyse patients by the actual treatment that was being taken while the event occurred.

Proprietary confidential information.

© 2016 Boehringer Ingelheim International GmbH or one or more of its affiliated companies. All rights reserved.

This document may not - in full or in part - be passed on, reproduced, published or otherwise used without prior written permission.

In addition, a sensitivity analysis will be performed that censors patients who switch from dabigatran to non-study warfarin or from study warfarin to non-study NOAC, at the time of the switch. The proportional hazards assumption will be investigated.

Kaplan-Meier curves will also be presented.

Subgroup analyses are planned and will be specified in the Trial Statistical Analysis Plan (TSAP).

7.3.2 Secondary analyses

Secondary efficacy endpoints (all time to first event, measured from date of randomisation to end of observation period) are:

- A combined endpoint of thrombotic events or death (DTE: all death + MI + stroke/SE) and unplanned revascularisation by PCI/CABG
- A combined endpoint of thrombotic events or death (DTE: all death + MI + stroke/SE)
- All death
 - Cardiovascular death
 - Non-cardiovascular death
 - Undetermined
- MI
- Stroke
- SE
- Stent thrombosis
- Composite of death + MI + stroke
- Unplanned revascularisation by PCI/CABG

Time to first event endpoints will be analysed using the same methods as for the primary endpoint. No multiplicity adjustments are planned for secondary endpoints (apart from those mentioned in the hierarchy, see [Section 7.2](#)). Nominal one-sided p-values will be reported for descriptive purposes.

All secondary analyses will be performed on the FAS. The robustness of these analyses will be assessed by on-treatment analyses (see [Section 7.3.1](#)).

TIA (further endpoint, see [Section 5.3.1](#)) will be analysed using the same approaches as above.

7.3.3 Safety analyses

Safety endpoints are defined in [Section 5.2.1](#).

These endpoints will be analysed using the same methods as the primary endpoints. No multiplicity adjustments are planned for safety endpoints (apart from those mentioned in the hierarchy, see [Section 7.2](#)).

Proprietary confidential information.

© 2016 Boehringer Ingelheim International GmbH or one or more of its affiliated companies. All rights reserved.

This document may not - in full or in part - be passed on, reproduced, published or otherwise used without prior written permission.

Adverse events will be coded using the Medical Dictionary for Regulatory Activities (MedDRA) coding dictionary. Standard BI summary tables and listings will be produced to compare the incidence of AEs. All AEs with an onset after the first dose of study medication up to the end of the REP of 6 days (see [Section 5.2.2.2](#)) after the last dose of study medication will be assigned to the treatment period for evaluation. Other adverse events will be assigned either to the screening or post study period as appropriate.

On-treatment analyses will be performed for AEs.

7.3.4 Interim analyses

No interim analysis is planned, but blinded sample size re-calculations may be performed. The conduct of the trial will be monitored by a DMC. The DMC will hold regular meetings to monitor imbalance in endpoints, with the focus on MBE/CRNMBE. The DMC's objectives and working practices are documented in the DMC charter.

The DMC may recommend terminating the study at any time for DE-DAT safety concerns. Further details will be included in the DMC charter.

The DMC will have unblinded safety reviews every 2 months.

7.3.5 Pharmacokinetic analyses

Not applicable.

7.3.6 Pharmacodynamic analyses

Not applicable.

7.3.7 Pharmacogenomic analyses

Not applicable.

7.4 HANDLING OF MISSING DATA

A major goal of the trial is to obtain virtually complete follow-up of vital status. As mentioned in [Section 7.3.1](#), all patients lost to follow-up will be treated as censored at the time of last known vital status.

The CTR will contain a summary of the number and proportion of patients with (and without) complete follow-up of vital status in each treatment group.

Partial dates will be imputed for the primary and secondary endpoints. Specific imputation rules will be documented in the TSAP.

7.5 RANDOMISATION

Patients aged <80 years old will be randomly assigned to 110mg DE-DAT, 150mg DE-DAT or warfarin-TAT in a 1:1:1 ratio for the duration of the trial.

Proprietary confidential information.

© 2016 Boehringer Ingelheim International GmbH or one or more of its affiliated companies. All rights reserved.

This document may not - in full or in part - be passed on, reproduced, published or otherwise used without prior written permission.

Patients aged ≥ 80 years old will be randomly assigned depending on their geographical region:

- Patients aged ≥ 80 years old in the USA will be assigned to 110mg DE-DAT, 150mg DE-DAT or warfarin-TAT in a 1:1:1 ratio
- All other patients aged ≥ 80 years old (i.e. EU/ROW) will be assigned to 110mg DE-DAT or warfarin-TAT in a 1:1 ratio.

Patients will be randomised in permuted blocks, dynamically stratified by age (< 80 or ≥ 80 years old) and region (EU/ROW or USA) using an IRT. Dynamic stratification allocates blocks of randomisation numbers according to the strata of the first randomised patient within that block. For example, if the first patient randomised to the first block is < 80 years old and from the USA, other randomisation numbers within this block will only be allocated to patients < 80 years old from the USA (until there are no more randomisation numbers left to allocate within this block). BI will arrange for the packaging and labelling of study medication. The randomisation list will be generated using a validated system and a pseudo-random number generator so that the resulting treatment will be both reproducible and non-predictable. The block size will be documented in the CTR. Access to the codes will be controlled and documented.

7.6 DETERMINATION OF SAMPLE SIZE

This is an event-driven trial where it is assumed that the first patient recruited into the study will be followed up for a maximum of approximately 30 months and the last patient recruited into the trial will be followed up for a minimum of 6 months. It is assumed that patient accrual will be approximately uniform over the 24 month recruiting period.

The proportion of patients with at least one MBE/CRNMBE at one year is estimated to be 14% based on current blinded trial data.

A relative NI margin for the original co-primary endpoint (DTE) was chosen in analogy to recent SPAF trials with primary endpoints of stroke/SE, where 1.38 was used by the FDA for ximelagatran, apixaban, rivaroxaban and dabigatran to preserve at least 50% of the relative reduction (on the log scale) in the risk associated with warfarin in six previous (historical), randomised, controlled trials. See publication by Jackson K, Gersh BJ, Stockbridge N, et al. [[R08-2662](#)]. The same NI margin has been applied to MBE/CRNMBE as it was considered the most clinically relevant available reference in the absence of any other type of data.

The overall sample size is driven by the non-inferiority comparison of MBE/CRNMBE between 110mg DE-DAT or 150mg DE-DAT and warfarin-TAT. With $\alpha=0.025$ (one-sided) and 14% of patients with at least one event at one year, 334 patients with at least one MBE/CRNMBE in each pair of treatment groups (i.e. 167 patients with MBE/CRNMBE per treatment group) are required to achieve 83.6% power for this endpoint, yielding a final sample size estimated at 834 patients in each treatment group (i.e. 2502 randomised patients in total). Therefore approximately 500 patients with at least one MBE/CRNMBE are required in total across the three treatment groups.

Proprietary confidential information.

© 2016 Boehringer Ingelheim International GmbH or one or more of its affiliated companies. All rights reserved.

This document may not - in full or in part - be passed on, reproduced, published or otherwise used without prior written permission.

As described in [Section 7.3.1](#), for the comparison of 150mg DE-DAT vs warfarin-TAT, patients from the EU/ROW who are ≥ 80 years old will be excluded from the warfarin-TAT arm (as patients who are ≥ 80 years old from the EU/ROW are not randomised to 150mg DE-DAT). The actual number of patients entered may increase or decrease based upon actual event rates. As this is an event-driven trial, the trial can conclude earlier, if an adequate number of events are reported sooner or later, if more events are needed. Because the last patient entered must be followed up for a minimum of 6 months and to avoid accruing too many events, recruitment will need to be stopped before the required number of events are observed. Blinded event rates will be monitored closely by BI (and the Executive Steering Committee) to predict the time at which recruitment should be stopped. Sites will be notified when recruitment ends.

Proprietary confidential information.

© 2016 Boehringer Ingelheim International GmbH or one or more of its affiliated companies. All rights reserved.

This document may not - in full or in part - be passed on, reproduced, published or otherwise used without prior written permission.

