© 2016 Boehringer Ingelheim International GmbH or one or more of its affiliated companies. All rights reserved.

This document may not - in full or in part - be passed on, reproduced, published or otherwise used without prior written permission.

[figure not shown]

Figure 3.1: 1 Study Plan

Prior to consent, the patient's antithrombotic treatment (i.e. ASA and anticoagulant use before and during PCI, use of clopidogrel or ticagrelor loading dose) should be managed as per local standard of care. The screening period will consist of one visit (Visit 1). The patients will be randomised at Visit 2. Screening and randomisation can be conducted on the same day. The treatment period will consist of between three and 10 visits (Visits 3-12). The trial is event driven and is designed to continue until approximately 500 patients with at least one MBE or CRNMBE (in total) occur. The last patient randomised will receive at least six months of treatment and patients recruited earlier remain in the study until the time point at which this last patient has reached at least six months. Any ongoing patient, at the time the required number of events is reached will be discontinued. Following completion of the treatment period, the patients will have a follow-up visit four weeks later.

The visits scheduled at 15, 21 and 27 months (Visits 8, 10 and 12) are to be conducted by telephone. Collection of AEs, outcome events (OE) (including bleeding) and use of concomitant medication will be made.

Blood sampling for a standard chemistry safety panel (including renal function and Liver Function Tests (LFTs)) will be collected at Visits 1, 2, 3, 5, 7 and End of treatment (EOT). In addition, samples for standard haematology safety panel will be taken at all clinic visits. All

Proprietary confidential information.

© 2016 Boehringer Ingelheim International GmbH or one or more of its affiliated companies. All rights reserved.

This document may not - in full or in part - be passed on, reproduced, published or otherwise used without prior written permission.

blood measurements (with the exception of INR and screening labs) will be performed by a central laboratory.

For further study procedure details see [Flow Chart](#).

The end of the trial is defined as “last patient out”, i.e. last visit completed by the last patient.

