7.2 NULL AND ALTERNATIVE HYPOTHESES

Two safety hypotheses (110mg Dabigatran Etexilate (DE-DAT) vs. warfarin-TAT and 150mg DE-DAT vs. warfarin-TAT) will be tested:

1. 110mg DE-DAT is non-inferior to warfarin-TAT with respect to MBE/CRNMBE over the duration of the trial
2. 150mg DE-DAT is non-inferior to warfarin-TAT with respect to MBE/CRNMBE over the duration of the trial.

To control the Type I error rate at a one-sided 0.025 level, a hierarchical procedure for multiple testing will be used to test the above hypotheses. Additional testing for safety and efficacy endpoints will also be included in this hierarchical procedure. The following hierarchical procedure will be applied:

Step 1 – Non-inferiority of 110mg DE-DAT to warfarin-TAT in MBE/CRNMBE is met at the one-sided 0.025 level of significance

Step 2 – Non-inferiority of 150mg DE-DAT to warfarin-TAT in MBE/CRNMBE is met at the one-sided 0.025 level of significance

Step 3 – Non inferiority of 150mg DE-DAT and 110mg DE-DAT combined to warfarin-TAT in DTE and unplanned revascularisation by PCI/CABG is met at the one-sided 0.025 level of significance

Proprietary confidential information.

© 2016 Boehringer Ingelheim International GmbH or one or more of its affiliated companies. All rights reserved.

This document may not - in full or in part - be passed on, reproduced, published or otherwise used without prior written permission.

Step 4 – Superiority of 110mg DE-DAT to warfarin-TAT in MBE/CRNMBE is met at the one-sided 0.025 level of significance

Step 5 – Non inferiority of 150mg DE-DAT and 110mg DE-DAT combined to warfarin-TAT in DTE is met at the one-sided 0.025 level of significance

Step 6 – Superiority of 150mg DE-DAT to warfarin-TAT in MBE/CRNMBE is met at the one-sided 0.025 level of significance

If any of the steps above fail to meet statistical significance, the testing procedure will stop at that step and subsequent tests will not be performed.

The Non-Inferiority (NI) margin used for MBE/CRNMBE will be 1.38 (on the relative HR scale). See [Section 7.6](#) for a clinical justification of this margin. The upper bound of the Wald confidence interval (CI) of the HR of DE-DAT vs. warfarin-TAT (one-sided 97.5%) will be compared to this NI margin for the NI testing.

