4. CHANGES IN THE PLANNED ANALYSIS OF THE STUDY

During the course of the study, the DMC may advise to stop enrolment into certain treatment arms or to stop the study completely. For further information, see CTP [5], Section 7.3.4. Changes to the planned analysis were introduced in protocol amendments 1 and 2. In addition, some further changes were implemented as follows.

Due to the Japanese local amendment (where the randomisation age group stratification factor was changed from <80 or ≥80 years old to <70 or ≥70 years old for Japanese patients), it will be necessary to change the way the age group stratification factor is defined in the analysis. Instead age group will be changed to be non-elderly vs. elderly and this will be used as the stratification factor in some analyses.

Due to the relatively few numbers of elderly patients finally recruited in the US region, it will not be possible to fit an age-group stratified Cox proportional hazards regression model for the 150mg DE-DAT versus warfarin-TAT comparison for any of the endpoints. Instead an unstratified model will be applied comparing 150mg DE-DAT versus warfarin-TAT. (excluding elderly EU/ROW patients in the warfarin-TAT group). In addition, unstratified sensitivity analyses of the non-elderly stratum only will be conducted.

GI bleeds, MBEs (ISTH), CRNMBEs, life-threatening bleeds and fatal bleeds were added as other safety endpoints.

The further endpoint of hospitalisation and the further composite endpoint of all-cause death or hospitalisation were added at the request of the Executive Steering Committee on 22nd November 2016.

The sensitivity analysis that censors patients who switch from study dabigatran to non-study NOAC/VKA or from study warfarin to non-study NOAC/VKA, at the time of the switch plus the Residual Effect Period (REP) of 6 days will not be performed because it will be virtually identical to the on-treatment sensitivity analysis already planned.

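### The 83.6% power and 834 patients per arm do not hold for 150mg versus warfarin, because elderly non-US patients are left out of that comparison and the event target ignores this

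*Protocol*

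**What the plan says.** Protocol 7.6 bases the sample size on non-inferiority of either dose to warfarin on MBE/CRNMBE. It asks for 334 patients with an event in each pair of arms ("i.e. 167 patients with MBE/CRNMBE per treatment group) are required to achieve 83.6% power for this endpoint"). From this it takes 834 patients per arm, 2502 in total and about 500 events over the three arms. The synopsis repeats 2502 and 834, marked as approximations. Section 3.1 makes the total the stopping rule: the trial is "designed to continue until approximately 500 patients with at least one MBE or CRNMBE (in total) occur".

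Allocation is not equal for everyone. Under Protocol 7.5, patients under 80, and US patients of any age, are randomised 1:1:1. Patients aged 80 or over elsewhere "will be assigned to 110mg DE-DAT or warfarin-TAT in a 1:1 ratio". For the 150mg comparison, 7.3.1 and 7.6 say that these patients "will be excluded from the warfarin-TAT arm". SAP section 4 reports that for Japanese patients "the randomisation age group stratification factor was changed" to a cut at 70 years, and SAP 7.4 keeps the exclusion for the 150mg model. Neither document gives a separate event count, arm size or power for the 150mg comparison.

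**The concern.** The exclusion is stated in the paragraph after the calculation, but nothing in the calculation changes because of it. Every elderly non-US patient enrolled counts towards 2502, and every bleed in that group counts towards 500. None of them contributes to 150mg versus warfarin. The 150mg pair must therefore fall short of 334 events, and the 150mg arm short of 834 patients, while the 110mg pair exceeds both figures.

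Non-inferiority of 150mg is one of the two primary hypotheses. It is Step 2 of the hierarchy, so failure there ends testing of both efficacy non-inferiority hypotheses and of superiority on bleeding for either dose. A reader would judge such a failure against 83.6% power, which the planned total does not provide for this comparison.

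**Working it through.** **Inputs**
- One-sided alpha of 0.025, margin 1.38 on the hazard ratio scale (Protocol 7.2).
- 14% of patients with an event at one year, uniform accrual over 24 months, follow-up from 6 to 30 months (Protocol 7.6).
- Stopping at about 500 events in total (Protocol 3.1, 7.6).
- True hazard ratio of 1. This is not stated, but it is implied by "i.e. 167 patients with MBE/CRNMBE per treatment group" and reproduces the stated power.
- e, the share of randomised patients who are elderly and non-US. The documents do not give it; 5% to 25% is assumed.

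**Reproducing the plan's figures**

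Power = Φ(√(d/4) × ln 1.38 − 1.96), with ln 1.38 = 0.3221.
- d = 334: √83.5 = 9.138; 9.138 × 0.3221 = 2.943; Φ(0.983) = 83.7%. The plan states 83.6%, which is what 333 events (500 × 2/3) give.
- Hazard = −ln(0.86) = 0.151 per year. With follow-up uniform on 0.5 to 2.5 years, the event probability is 0.1994. Then 834 × 0.1994 = 166 events per arm (plan: 167) and 2502 × 0.1994 = 499 in total (plan: about 500).
- 334 × 3/2 = 501. Moving from 334 per pair to about 500 in total works only if the three arms are equal and all patients enter every comparison.

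**Applying the stated randomisation**

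Of the eligible share (1−e), one third goes to each arm. Of the share e, half goes to 110mg and half to warfarin. With 2502 patients and 500 events at equal rates:
- 150mg arm = 834(1−e); 110mg and warfarin arms = 834(1 + e/2) each.
- 150mg pair events = 500 × (2/3)(1−e) = 333(1−e).
- 110mg pair events = 333(1 + e/2).

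| e | Arms 110 / 150 / warfarin | 150mg pair events | 150mg power | 110mg pair events | 110mg power |
|---|---|---|---|---|---|
| 5% | 855 / 792 / 855 | 317 | 81.7% | 342 | 84.5% |
| 10% | 876 / 751 / 876 | 300 | 79.7% | 350 | 85.4% |
| 15% | 897 / 709 / 897 | 283 | 77.4% | 358 | 86.2% |
| 20% | 917 / 667 / 917 | 267 | 74.9% | 367 | 86.9% |
| 25% | 938 / 626 / 938 | 250 | 72.1% | 375 | 87.7% |

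The warfarin column counts everyone randomised to warfarin; the number analysed against 150mg equals the 150mg arm. Power for 150mg passes below 80% at about e = 9%. Up to about e = 5% the loss stays under 2 points.

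**If the elderly bleed more often**

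Suppose, as a further assumption, that the elderly have 1.5 times the hazard. Their event probability is then 0.282, against 0.199 for the others, and more of the 500 events fall outside the 150mg pair. The pair has 500 × (2/3) × 0.199(1−e) / [0.199(1−e) + 0.282e] events. Power is 81.0%, 78.0%, 74.9%, 71.5% and 67.9% for e = 5%, 10%, 15%, 20% and 25%.

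**Total needed to give the 150mg pair 334 events (equal rates)**

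501/(1−e): about 557 at e = 10% and about 626 at e = 20%, against the planned 500.

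**The case against.** The sentence on power is correct if read as conditional: a pair with 334 events does have about 83.6% power. The fault lies in the step to about 500 in total. That step is part of the same calculation, though, and it sets the stopping rule, so the condition is not met for 150mg.

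The plan also has flexibility. The synopsis calls its numbers approximations, 7.3.4 allows blinded sample size re-calculation, and the flow chart notes, 6.1 and 7.6 let the trial run longer or enrol more. The synopsis and 7.6 tie changes in patient numbers to event rates, and none of these provisions is tied to the allocation. Enrolling more patients in the same mix and still stopping at 500 events leaves the 150mg shortfall where it was.

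Three points stand. The size of the loss depends on e, which is unknown, and it is small if e is below about 5%. The 1.5-fold elderly hazard has no figure in the documents behind it. And a true hazard ratio below 1 raises power: with 250 events, the formula with ln(1.38/HR) gives 83.9% at 0.95 and 92.2% at 0.90. So a practically underpowered test is not shown. What is shown is that the stated figure, which is the figure for a hazard ratio of 1, does not apply to this comparison. Finally, Step 2 is decided by a confidence bound against 1.38, so type I error and bias are not affected.

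**Conclusion.** The concern holds. For any e above zero, 2502 patients and 500 total events give fewer than 834 patients in the 150mg arm and fewer than 334 events in its comparison, so 83.6% overstates its power. The direction follows from the protocol's own randomisation and exclusion rules. The size rests on the assumed e, a true hazard ratio of 1 and equal event rates: 79.7% at 10%, 74.9% at 20%, 72.1% at 25%, and lower if the elderly bleed more. The lower Japanese age cut reported in the SAP widens the excluded group; the local amendment behind it was not among the documents, and none of the figures here depends on it.

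**What to change.** In Protocol 7.6 and the synopsis, replace the single statement of 83.6% per pair and 834 per arm with separate figures for each comparison, using the share of elderly non-US patients taken from blinded data. For each comparison give the expected arm sizes, the expected events at 500 in total, and the resulting power. At equal rates and e between 10% and 25%, that is about 85% to 88% for 110mg and about 72% to 80% for 150mg.

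In the blinded event monitoring, also report the number of events among patients eligible for the 150mg comparison. Eligibility depends only on age and region, so this can be done without unblinding.

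The cost is wording and one extra line in the monitoring report. No patients are added, and the hypotheses, margin and analysis do not change. The stated 150mg power becomes less favourable, and this change does not restore it. Restoring it would need a larger event total, about 626 at e = 20%, which is a separate decision for the sponsor.

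### The 83.6% power in Protocol 7.6 is a correct per-pair figure, but it is not the power the design has for the 150mg hypothesis, which is about 74% at a true hazard ratio of 1 and lower once elderly EU/ROW patients are excluded

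*Protocol*

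**What the plan says.** Protocol 7.6 sizes the trial on one pairwise comparison and applies it to either dose: "The overall sample size is driven by the non-inferiority comparison of MBE/CRNMBE between 110mg DE-DAT or 150mg DE-DAT and warfarin-TAT". It asks for 334 events per pair ("i.e. 167 patients with MBE/CRNMBE per treatment group"), which "are required to achieve 83.6% power for this endpoint", and concludes that "approximately 500 patients with at least one MBE/CRNMBE are required in total across the three treatment groups". Protocol 3.1 uses the same total of about 500 as the point to which the trial runs.

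Protocol 7.2 sets the order of testing: "To control the Type I error rate at a one-sided 0.025 level, a hierarchical procedure for multiple testing will be used". Step 1 is non-inferiority of 110mg, Step 2 is non-inferiority of 150mg, and "If any of the steps above fail to meet statistical significance, the testing procedure will stop at that step". SAP 7.4 repeats the sequence. Protocol 2.2 gives non-inferiority of each dose as the aim.

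Under Protocol 7.5, patients aged 80 or over outside the USA are never randomised to 150mg. Protocol 7.3.1 and 7.6 and SAP 7.4 remove the corresponding warfarin patients from the 150mg comparison. SAP 4 and 7.4 set the elderly cut at 70 in Japan. Neither document gives a power for 150mg within the sequence, or adjusts the 334 events for the exclusion.

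**The concern.** A reader of 7.6 would take 83.6% as the chance of showing non-inferiority for 110mg and, equally, for 150mg. Only the 110mg test is performed unconditionally. 150mg can be declared non-inferior only if both tests pass, and its own pair is short of the 334 events behind the quoted power.

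At stake is how the design is described, and how a failed or unreached Step 2 would later be read. Steps 3 to 6, which include both efficacy non-inferiority tests and both superiority tests, can be reached only through Step 2, so none can have a higher probability of success than Step 2 has in the sequence.

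**Working it through.** **Inputs.** Margin 1.38 and one-sided 0.025 per step (Protocol 7.2); 334 events per pair, 167 per arm, about 500 in total (7.6). The true hazard ratio is not stated; 1 is inferred because it reproduces the plan's figure. The elderly EU/ROW share of events is not in the documents and is shown as a range.

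**1. The plan's figure.** For a pair with equal events, power = Φ(ln 1.38 × √(events/4) − 1.96). With 334 events: ln 1.38 = 0.3221, √83.5 = 9.138, product 2.943, so Φ(0.983) = 83.7%. With 500 × 2/3 = 333.3 events it is 83.65%. The stated 83.6% is reproduced.

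**2. Steps 1 and 2 together, before the exclusion.** Each log hazard ratio has variance 2/167 and the two share the warfarin arm (covariance 1/167), so their correlation is 0.5. The bivariate normal probability that both pass is 73.9%. Independent tests would give 0.837² = 70.1%; the shared control raises this. A simulation of 40,000 trials with three arms of 834, exponential event times and Wald intervals gave 73.8%. Given that Step 1 passes, Step 2 passes with probability 0.739/0.837 = 88%.

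**3. The exclusion, with 500 events in total.** Let p be the share of all events in elderly EU/ROW patients. They are split between two arms and the remaining events among three.
- 150mg pair: 500 × (1 − p) × 2/3 events.
- 110mg pair: 500 × [(1 − p) × 2/3 + p] events.
- The covariance of the two log hazard ratios is 1/(all warfarin events), so the correlation is ½ × √(warfarin events in the 150mg comparison / all warfarin events).

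| p (assumed) | Events, 150mg pair | 150mg alone | Events, 110mg pair | 110mg alone | Correlation | Steps 1 and 2 |
|---|---|---|---|---|---|---|
| 0 | 333 | 83.7% | 333 | 83.7% | 0.50 | 73.8% |
| 10% | 300 | 79.7% | 350 | 85.4% | 0.46 | 71.7% |
| 20% | 267 | 74.9% | 367 | 86.9% | 0.43 | 68.4% |
| 30% | 233 | 69.1% | 383 | 88.4% | 0.39 | 64.1% |

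With a fixed total, the excluded patients' events go to the 110mg pair. Step 1 gains slightly, but the probability of passing both steps still falls.

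**4. Sensitivity to the true hazard ratio** (334 events per pair, no exclusion, same value for both doses). Steps 1 and 2 together: 95.3% at 0.90, 87.4% at 0.95, 73.9% at 1.00, 37.9% at 1.10.

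**The case against.** The strongest reply is that 7.6 ties 83.6% openly to a pair of treatment groups, that the figure is right, and that quoting per-comparison power beside a published test order is common. This stands: a reader might infer that the sample size was miscalculated, and the documents do not support that. What is missing is the figure for 150mg.

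Secondly, a reader might infer that the trial carries a 26% risk of failing its 150mg hypothesis. That holds only if both true hazard ratios are 1, a value the protocol does not state. Its rationale points lower: the cited randomised comparison of dual with triple therapy reports a hazard ratio of 0.36, and Steps 4 and 6 test superiority. At 0.90 the joint probability exceeds 95% before the exclusion. The reply stands as a limit on the 74%. It does not rescue 83.6% as the 150mg figure, because 83.6% rests on the same value of 1.

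Thirdly, the size of the elderly effect is unknown. The share that matters is of events, not patients, and the two may differ because Protocol 4.2.2.1 notes higher bleeding risk from age 75 with antiplatelets. So the percentages in the table are illustrations only. The direction holds for any non-zero share with the total held at about 500.

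Fourthly, 500 is approximate, 7.6 discloses the exclusion and allows the trial to run longer, and 7.3.4 permits blinded re-calculation. If 334 events were kept in the 150mg pair, Steps 1 and 2 together would reach about 77% or 80% at a 10% or 20% share. But the documents set the target as a total, and nothing in them requires 334 events in that pair.

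**Conclusion.** The concern holds as a matter of what 83.6% describes. It is the power of one stand-alone pairwise test with 334 events at an implied true hazard ratio of 1. On that same assumption, with equal events per arm, the probability of declaring 150mg non-inferior under the fixed sequence is about 74%, roughly 10 percentage points lower. The elderly EU/ROW exclusion lowers it further by an amount the documents do not allow one to fix: to about 72% or 68% if those patients carry 10% or 20% of events.

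It would also be inexact to say that 83.6% belongs to Step 1 alone, since with 500 events in total Step 1 has about 85% or 87% at those shares. Type I error control is unaffected, and nothing here shows that the trial is too small for its purpose.

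**What to change.** In Protocol 7.6:
- state that 83.6% is the per-pair power at a true hazard ratio of 1 with 334 events;
- add that the probability of passing Steps 1 and 2 is about 74% under the same assumption, before the elderly exclusion;
- state that, with about 500 events in total, the 150mg pair will have fewer than 334 events and lower power, and compute that power from the blinded observed share of events in elderly EU/ROW patients rather than from an assumed share.

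The cost is a few sentences and a less favourable stated figure. Sample size, margin, test order and analyses stay as they are.
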